5.1.7 Time in study

Time in study (years) is derived as $(\text{EOS date} - \text{randomization date} + 1 \text{ day}) / 365.25$.

Time in study (months) is derived as $(\text{EOS date} - \text{randomization date} + 1 \text{ day}) / 30.4375$.

5.2 Subject characteristics

5.2.1 Demographics

The following demographic variables are derived:

- Sex, from the ‘Demographics’ eCRF (Male, Female)
- Age (years), from the ‘Demographics’ eCRF; if available, ‘Age at re-screening’ overwrites the initially entered ‘Age’
- Age categories derived from the above as follows: < 18, 18–30, 31–40, 41–55, and ≥ 56 years. Age high-level categories: < 40, and ≥ 40. Age categories as per EudraCT requirement: < 12, 12–17, 18–64, 65–84, and ≥ 85
- Height (cm), from the ‘Height & Body Weight’ eCRF
- Weight (kg), from the ‘Height & Body Weight’ or from the ‘Body Weight’ eCRF:

The latest measurement available prior to study treatment start date is selected. If first intake is not documented, use the latest measurement available prior to randomization. If neither date is available (for screen failures), the latest weight assessment available is used.

- Body mass index (BMI; kg/m^2) derived as $\text{Weight (kg)} / (\text{Height (cm)} / 100)^2$
- BMI categories: < 18.5, ≥ 18.5 – < 25, ≥ 25 – < 30, and ≥ 30
- Race, from the ‘Demographics’ eCRF (Black or African American, American Indian or Alaska Native, Asian, Native Hawaiian or Other Pacific Islander, White, Other, and Not applicable)
- Ethnicity, from the ‘Demographics’ eCRF (Hispanic or Latino, Not Hispanic or Latino, and Unknown)
- Country based on site mapping performed on SDTM level
- Geographical region of site, countries are assigned to the following regions:
 - European Union (EU) + UK: Austria, Belgium, Bulgaria, Czech Republic, France, Germany, Greece, Hungary, Italy, Poland, Portugal, Spain, United Kingdom
 - Europe Non-EU + Russia: Russian Federation
 - North America: Canada, United States
 - Rest of World: Mexico

5.2.2 Baseline disease characteristics

Baseline characteristics variables are defined as follows:

Stratification variables from IRT

- **Baseline EDSS (from IRT)** (≤ 3.5 , > 3.5) from the IRT system

Baseline disease characteristics variables from eCRF / non-IRT external data

- **Baseline EDSS score**, defined as the latest available EDSS score as entered in the EDSS/FS eCRF (i.e., not re-derived based on sub-scores) prior to or on the date of randomization
- **Baseline EDSS (from eCRF)**, categorized as (≤ 3.5 , > 3.5), derived from the baseline EDSS score
- **Time since first symptoms (years)**, defined as [Date of randomization – Date of first MS symptoms + 1] in days / 365.25. Taken from ‘MS History – Disease Characteristics’ eCRF at screening. Partial dates of first MS symptoms are imputed to the 1st day of the month (if the day is missing) and to the 1st of January (if the day and month are missing). No imputation is performed if the date is completely missing.
- **Time since initial diagnosis (years)**, defined as: [Date of randomization – Date of initial diagnosis + 1] in days / 365.25. Taken from ‘MS History – Disease Characteristics’ eCRF at screening. Partial dates of initial diagnosis are imputed to the maximum of [Date of first MS symptoms, 1st day of the month] (if the day is missing) and to the maximum of [Date of first MS symptoms, 1st of January] (if the day and month are missing). No imputation is performed if the date is completely missing.
- **MS subtype (RRMS / SPMS)**, relapsing-remitting multiple sclerosis [RRMS], secondary progressive multiple sclerosis [SPMS] with superimposed relapses. Taken from ‘MS History – Disease Characteristics’ eCRF at screening; subtype at re-screening overwrites the initially entered subtype.
- **Time since most recent relapse (months) at screening**, defined as [Date of screening – Onset date of latest MS relapse prior to screening + 1] in days / 30.4375. From eCRF form ‘MS History - Relapse’ at screening. Take the most recent “Onset date of previous relapse” among all previous relapses entered on the ‘MS History - Relapse’ eCRF. Partial onset dates are imputed to the maximum of [Date of first MS symptoms, 1st day of the month] (if the day is missing) and to the maximum of [Date of first MS symptoms, 1st of January] (if the day and month are missing). Data collected at re-screening overwrites the initially entered data.
- **Number of relapses in the year prior to study entry**, as reported in the corresponding question on the ‘MS History - Relapse’ eCRF (i.e., not based on recorded onset dates of previous relapses). Data collected at re-screening overwrites the initially entered data.
- **Number of relapses in the 2 years prior to study entry** as reported in the corresponding question on the ‘MS History - Relapse’ eCRF (i.e., not based on recorded onset dates of previous relapses). Data collected at re-screening overwrites the initially entered data.
- **Prior MS treatment other than DMF (yes/no)** (‘yes’ if any MS treatment recorded on then ‘MS Specific Treatment History’ eCRF form or as prior concomitant medications on the

‘Study-concomitant therapy - Disease-modifying treatment for MS’ eCRF; otherwise ‘no’ if no such medications are recorded).

- **Months on DMF at screening** defined as [Date of screening – DMF start date] in days / 30.4375. DMF start date is defined as the earliest DMF start date documented in the Drug Log – DMF eCRF. In case of partially missing DMF start date, the start date is imputed to the latest possible date, see Section 12.1.1 for full details.
- **Relapses in the previous 6 months prior to study entry while on treatment with DMF (0, 1, ≥ 2)** number of relapses recorded in the 6 months prior to date of screening based on recorded onset dates of previous relapses (‘MS History – Relapse’ eCRF form) and recorded start/end dates of DMF treatment.
- **Presence of T1 Gd+ lesions (yes/no) in the previous 12 months prior to study**, as provided by sites (yes/no) - (‘MS history - MRI’ eCRF form).
- **Presence of T1 Gd+ lesions (yes/no)** on baseline MRI scan as provided by the MRI central reading.
- **Number of documented T1 Gd+ lesions** on baseline MRI scan as provided by the MRI central reading.
- **Presence of new or enlarging T2 (yes/no) in the previous 12 months prior to study**, as provided by sites (yes/no) - (‘MS history - MRI’ eCRF form).
- **Volume of T2 lesions** on baseline MRI scan as provided by the MRI central reading.
- **Smoking status** (Current smoker, Former smoker, Never smoked), taken from ‘Smoking status’ eCRF.

Note: For re-screened subjects, information for baseline characteristics ‘at screening’ is taken from the last Re-screening Visit, if available, instead of the Screening Visit.

Handling of missing/partial dates: In case of partial dates for required dates (MS symptoms, initial diagnosis, latest MS relapse prior to Screening), the lower limit is used in derivations. Missing dates are not replaced; the corresponding variable is considered missing.

5.2.3 Previous and concomitant therapies

Therapies are collected in the following CRF pages: ‘Previous Medications’, ‘Concomitant Medications’, ‘Interferon beta-1a history’, ‘Interferon beta-1b history’, ‘Glatiramer acetate history’, ‘Natalizumab history’, ‘Mitoxantrone history’, ‘Alemtuzumab concentrate history’, ‘Teriflunomide history’, ‘Daclizumab history’, ‘Ocrelizumab history’, ‘Cladribine history’, ‘Other MS Specific Treatment History’, ‘Study-concomitant therapy - Disease-modifying treatment for MS’, ‘Corticosteroids for Treatment of Relapse’.

Terms are coded using the World Health Organization (WHO) drug code dictionary (WHODRUG) and the anatomic therapeutic chemical (ATC) class code (version dated 1 March 2018 or later).

Handling of partial or missing start and end dates is detailed in Section 12.1.

5.2.3.1 Previous therapies

Previous therapies are therapies that were started and stopped prior to study treatment start date.

5.2.3.2 Treatment concomitant therapies

Includes all therapies that have been taken after study treatment start date up to EOT (last drug intake) + 15 days. This includes therapies ongoing at study start, as well as therapies starting after study treatment start date.

Handling of partial or missing start and end dates is detailed in Section 12.1.

5.2.3.3 Therapies starting after EOT

Includes all therapies that have been started after EOT (last drug intake). This includes therapies with start date from EOT + 1 day onwards.

Handling of partial or missing start and end dates is detailed in Section 12.1. Therapies with missing start date will be considered to have started on treatment.

5.3 Exposure and compliance

5.3.1 Study treatment exposure and compliance

Exposure and compliance with ponesimod / placebo information will be taken from the Study Drug Log eCRFs:

- **Up-titration Summary Ponesimod/Placebo eCRF** (collects information on up-titrations conducted as planned as per protocol, recording start and end date of up-titration);
- **Up-titration Ponesimod/Placebo eCRF** (collects information on up-titration if not conducted as planned as per protocol, separately for up-titration tablets on daily basis);
- **Maintenance Ponesimod/Placebo eCRF** (collects information on maintenance study drug intake based on maintenance tablets).

To derive the study treatment start date and time, in addition information collected on Study drug administration eCRFs ('Study Drug Administration - Day 1/Re-initiation', 'Study Drug Administration') is considered.

In addition, subjects filled an electronic study treatment diary (eDiary). Sites were instructed to review the entries in the subject study treatment diary versus the protocol-mandated drug intake regimen and versus the number of tablets dispensed and returned. Any discrepancy was to be clarified during the site visits, and actual drug intake was to be recorded in the eCRF, hence the

information from the eCRF is considered to be the most reliable, and all exposure derivations including derivation of EOT date are only based on eCRF data.

5.3.1.1 Study treatment exposure

Study treatment start date is defined as the earliest study drug start date documented in the study drug administration or study drug log eCRF pages, as listed above.

The time of study treatment start (time of first exposure to treatment) is taken from the study drug administration eCRF, where the date is equal to the study treatment start date, if available.

The EOT date is defined as the latest study treatment end date, as recorded on the Study Drug Log eCRFs listed above.

The following exposure variables are derived:

Duration of Study Treatment (days) = EOT date - Study treatment start date + 1 day. Duration of Study Treatment is also derived in weeks (days divided by 7), months (days divided by 30.4375), and years (days divided by 365.25).

Duration of Study Treatment is categorized as follows: ≤ 24 weeks (168 days), > 24 weeks to ≤ 48 weeks (336 days), > 48 weeks to ≤ 72 weeks (504 days), > 72 weeks to ≤ 96 weeks (672 days), > 96 weeks to ≤ 120 weeks (840 days), > 120 weeks to ≤ 144 weeks (1008 days), > 144 weeks (1008 days).

‘Study treatment exposure, interruptions excluded’ equals the ‘Number of days with intake documented’ for a subject overall as defined as part of the compliance derivations described in Section 5.3.1.2.1.

5.3.1.2 Compliance with study treatment

5.3.1.2.1 Compliance as percentage of days on study drug

Compliance is assessed as the percentage of days from the date of first intake until EOT with study drug intake documented in the eCRF:

$$\frac{\text{no. of days with intake documented}}{(\text{date of EOT-study treatment start date}) + 1 \text{ day}} \times 100$$

Note: Compliance below 100% is not necessarily indicative of a deviation from the protocol since the protocol mandates dose interruptions for certain very specific safety scenarios as well as based on investigator’s judgment.

For reporting, the calculated compliance is categorized as follows: 100%, 99% – $< 100\%$, 80% – $< 99\%$, 50% – $< 80\%$, $> 0\%$ – $< 50\%$, 0%.

The number of days with study drug intake documented is derived as follows:

During up-titration period

The number of days with intake documented is based on entries on the eCRF 'Up-titration Summary Ponesimod/Placebo' and/or 'Up-titration Ponesimod/Placebo'.

For subjects where the investigator confirmed the up-titration has been conducted as planned, the 'Up-titration Summary Ponesimod/Placebo' eCRF is filled, collecting only start and end date of the entire titration period without collecting 'number of tablets taken'. In that case the 'Number of days with intake documented' is derived and considered to be 'titration end date – titration start date + 1 day'.

For all other subjects, information is collected on the 'Up-titration Ponesimod/Placebo' eCRF, 'Treatment start date' resulting in potentially multiple records of up-titration drug intake (collecting in addition 'number of tablets taken'). In that case 'Number of days with intake documented' for each record is derived in the same way as during the maintenance period but based on the dose form with active drug only.

During maintenance period

As per protocol, one tablet of study drug is to be taken per day. On the 'Maintenance Ponesimod/Placebo' eCRF log form, each record collects 'Treatment start date', 'Treatment end date', and 'Number of tablets taken'. If, for a record, the 'Number of tablets taken' is \leq 'Treatment end date' – 'Treatment start date' + 1, it is assumed that the 'Number of tablets taken' represents the 'Number of days with intake documented' during that record's period of study drug intake. If, for a record, the 'Number of tablets taken' is $>$ 'Treatment end date' – 'Treatment start date' + 1, 'Number of days with intake documented' is set to 'Treatment end date' – 'Treatment start date' + 1 for the compliance calculation. These subjects are flagged as having taken $>$ 1 tablet per day on at least one occasion.

The 'Number of days with intake documented' for a subject overall is derived as the sum across all study drug log records (sum across up-titration, or maintenance records; multiple periods of study drug intake during up-titration or maintenance are possible, e.g., due to interruptions, or detailed up-titration eCRF filled).

The following deviations from the protocol-intended study drug maintenance are identified from the 'Maintenance Ponesimod/Placebo' eCRF log form and flagged on a subject basis:

- More than 1 tablet of study drug taken per day on at least one occasion (derivation see above);
- At least one occasion of treatment interruption of more than 3 days documented, but maintenance treatment resumed or started without up-titration. This includes occasions when maintenance treatment started more than 4 days after the day up-titrations stopped.

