2.1.1 Periods

The study consists of the following protocol defined periods:

- **Pre-randomization period** starts with signature of the Informed Consent Form (ICF) and ends with the subject's randomization and lasts up to 45 days (per screening attempt). Subjects can be re-screened once. It includes Visit 1 (Screening), Visit 2 (Baseline) and the pre-dose assessments of Visit 3 (Day 1).
- **Treatment period** starts on the day of randomization immediately after the first dose of study drug intake (Visit 3–Day 1 of the study). The double-blind treatment period has a variable duration from a minimum of 60 weeks (for the last subject randomized) to a maximum of 156 weeks (3 years) for the first subjects randomized in the trial. Average duration is expected to be approximately 2 years. It includes a randomization visit, visits at 2, 4, and 12 weeks after randomization, and 12-weekly visits thereafter until 60 weeks after the randomization of the last subject or 156 weeks of treatment (whichever occurs first). The treatment period consists of a titration and a maintenance phase.
 - A 2-week titration scheme is implemented on Day 1 (or at re-initiation following a treatment interruption of more than 3 days) to reduce the first-dose effects of ponesimod [see [Table 1](#)]. During the up-titration period, one tablet of ponesimod 2, 3, 4, 5, 6, 7, 8, 9, or 10 mg (or matching placebo) will be taken orally once daily.
 - The titration phase is followed by the maintenance phase with one tablet of ponesimod 20 mg (or matching placebo) administered orally once daily in the morning (from Day 15 to EOT).
- **Post-treatment period** starts immediately after the last dose of study treatment and ends when End-of-Study (EOS) visit has been completed. It comprises the post-treatment safety follow-up period and if applicable, is followed by the PTOP.
 - **Post-treatment safety follow-up period**
All subjects will enter the safety follow-up period which lasts for at least 30 days after the last dose of study treatment and includes a safety follow-up visit approximately 30 days after the last dose of study treatment (FU visit). Subjects participating in the lymphocyte subset sub-study will have an additional follow-up visit approximately 7 days after the last dose of study drug (FU7d visit).
 - **Post-treatment observation period**

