Subjects who prematurely discontinue study drug and complete the 30-day safety follow-up including the FU visit, will enter the PTOP which lasts until 60 weeks after randomization of the last subject or until Week 156, whichever is first (i.e., planned EOT visit) irrespective of treatment completion. The PTOP consists of an abbreviated schedule of assessments at the time of the originally scheduled 12-weekly visits (i.e., not all assessments are performed, see visit schedule). Safety follow-up visits are conducted in addition, following the post-treatment safety follow-up period schedule.

- **End-of-study:** the study level EOS occurs after all subjects have completed the safety follow-up period or the last visit of the PTOp. For an individual subject, EOS is reached when treatment, post-treatment safety follow-up, and if applicable, the PTOps have been completed:
 - For subjects who complete the treatment period, and for subjects who prematurely discontinue study treatment and do not enter the PTOp, the EOS visit corresponds to the 30-day follow-up visit (FU visit).
 - For subjects who prematurely discontinue study treatment and enter the PTOp period, the EOS visit corresponds to the last visit of the PTOp.

Table 1 **Dosing scheme**

Treatment period	Duration	Dose regimen in the ponesimod group
Titration	Day 1 and 2	2 mg
Titration	Day 3 and 4	3 mg
Titration	Day 5 and 6	4 mg
Titration	Day 7	5 mg
Titration	Day 8	6 mg
Titration	Day 9	7 mg
Titration	Day 10	8 mg
Titration	Day 11	9 mg
Titration	Day 12 to 14*	10 mg
Maintenance	Day 15 until EOT	20 mg

- * Visit 4 is to take place at Day 15 ± 1 day.
- EOT = End-of-Treatment.

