5.3.2 Study treatment adjustments or interruptions

Study-specific criteria for interruption and discontinuation of study treatment were pre-specified in the protocol section 5.1.12. The protocol did not allow any study treatment dose adjustments.

Study treatment interruptions are assessed via the compliance variables described in Section 5.3.1.2 and the assessment AEs leading to changes in study treatment as described in Section 5.5.5.

Subjects with at least one interruption: Derived as subjects with ‘Study treatment exposure, interruptions excluded’ < ‘Duration of Study Treatment’, based on the definitions in Section 5.3.1.1.

Total duration of interruption(s) (days) is derived as ‘Duration of Study Treatment’ – ‘Study treatment exposure, interruptions excluded’.

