9.5 Analysis of study treatment exposure and compliance

9.5.1 Study treatment exposure and compliance

9.5.1.1 Study treatment exposure

Exposure to study drug [defined in Section 5.3.1.1] is summarized using descriptive statistics for continuous and categorical data using the SAF. In addition, this table displays the overall subject year exposure (sum over all subjects' exposure). Tables are presented by treatment group. All variables are also presented in subject data listings, together with compliance, based on the SAF.

Subjects with at least one interruption as well as duration of interruptions will be summarized by treatment group on the SAF. Subject exposure to study drug is listed. Subjects with > 1 tablet taken on at least one day or maintenance treatment resumed without up-titration after an interruption of > 3 days are flagged.

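### Counting up-titration intake days from the active dose form only would, read literally, drop placebo-arm days recorded on the detailed up-titration form

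*SAP*

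**What the plan says.** Up-titration is a single-tablet scheme. Under SAP section 2.1.1, "one tablet of ponesimod 2, 3, 4, 5, 6, 7, 8, 9, or 10 mg (or matching placebo) will be taken orally once daily". Table 1 in the same section has maintenance starting on Day 15.

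Section 5.3.1 provides two up-titration forms, both shared by the arms. The summary form is for titrations done as planned. The detailed *Up-titration Ponesimod/Placebo* eCRF "collects information on up-titration if not conducted as planned as per protocol, separately for up-titration tablets on daily basis".

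Section 5.3.1.2.1 then sets three counting rules:

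- **Planned titration (summary form):** end date minus start date plus one day.
- **Titration not as planned (detailed form):** the number of days for each record "is derived in the same way as during the maintenance period but based on the dose form with active drug only".
- **Maintenance:** number of tablets taken, capped at the days the record spans.

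The subject's total is the sum over all records. It is divided by the days from first intake to EOT to give compliance. Section 5.3.1.1 reuses the same total as exposure with interruptions excluded. Section 5.3.2 flags a subject as interrupted when that total is below the treatment duration, and takes the difference as the interruption duration. Under section 9.5.1.1, "Subjects with at least one interruption as well as duration of interruptions will be summarized by treatment group on the SAF"; section 9.5.1.2 tabulates compliance by arm.

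**The concern.** The restriction to a dose form with active drug would make sense in a double-dummy design, where each subject takes two products and only one should be counted. The SAP describes no such design. With one tablet a day, the restriction excludes nothing in the ponesimod arm and every detailed-form up-titration record in the placebo arm. The SAP nowhere defines active drug to include placebo; elsewhere it uses *study drug* for both arms. The two neighbouring rules treat the arms alike, and only this one does not.

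At stake is a difference between arms created by the derivation. Placebo would look less compliant, less exposed once interruptions are removed, and more often or longer interrupted than ponesimod for identical tablet-taking.

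**Working it through.** The SAP states no figure on this point, so there is none to reproduce. The check applies its rules to an example.

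**Inputs**

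- Titration length, from Table 1: 2 + 2 + 2 + 1 + 1 + 1 + 1 + 1 + 3 = 14 days.
- Compliance (5.3.1.2.1) = 100 × documented days / D, where D = EOT date − start date + 1.
- Interruption days (5.3.2) = D − documented days.
- Compliance categories (5.3.1.2.1): 100%; 99% to <100%; 80% to <99%; 50% to <80%; >0% to <50%; 0%.
- Assumed: a placebo subject with one 14-day up-titration on the detailed form and one tablet taken every day. The values of D are also assumptions, shown as a range.

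**Literal rule, placebo.** Documented days = D − 14, or 0 if D ≤ 14.

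| D (days) | Documented days | Compliance | Category | Interruption days |
|---|---|---|---|---|
| 14 | 0 | 0/14 = 0% | 0% | 14 |
| 28 | 14 | 14/28 = 50.0% | 50% to <80% | 14 |
| 84 | 70 | 70/84 = 83.3% | 80% to <99% | 14 |
| 168 | 154 | 154/168 = 91.7% | 80% to <99% | 14 |
| 336 | 322 | 322/336 = 95.8% | 80% to <99% | 14 |
| 730 | 716 | 716/730 = 98.1% | 80% to <99% | 14 |
| 1092 | 1078 | 1078/1092 = 98.7% | 80% to <99% | 14 |

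The category boundaries follow directly. Compliance reaches 80% at D = 70 (56/70) and would reach 99% only at D = 1400 (1386/1400), beyond the 1092-day maximum. From 70 to 1092 days the subject therefore sits in 80% to <99% instead of 100%.

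**Ponesimod, same intake.** Documented days = D, compliance 100%, interruption days 0, at every D. With placebo tablets counted, the placebo subject gets the same result.

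**Two detailed-form up-titrations.** Up to 28 days are lost. The loss in percentage points is 28/168 = 16.7, 28/336 = 8.3, 28/730 = 3.8 and 28/1092 = 2.6. These are losses and not resulting compliance values, because a repeated titration normally follows a real gap.

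**With a true gap of g days.** The correct interruption duration is g and the literal one is g + 14 (one titration). The interruption flag is right either way; the duration is too long by 14 days.

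**The case against.** The strongest reply is that the phrase cannot mean what it literally says. Compliance is defined in 5.3.1.2.1 as days with study drug intake documented in the eCRF, the forms carry both ponesimod and placebo in their titles, and the total is summed over all study drug log records. Read together, these count placebo tablets. *Dose form* may also refer to a field on an eCRF that the reader cannot see. To set placebo records to zero, a programmer would probably need to bring in the treatment arm, which section 5.3.1 does not ask for. The wording may well be left over from another design.

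That is a fair account of how the phrase arose, but it does not rescue it. Under the benign reading the restriction excludes nothing and has no function; under the literal reading it contradicts the definition it is meant to implement. It needs correcting either way.

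The objection on scale largely stands. The detailed form is used only when titration departed from plan, and some of those subjects will have a true gap and would be flagged as interrupted anyway. Perfect daily intake on that form is a narrow case, such as tablets taken out of sequence or treatment stopped during titration. The outputs are descriptive, in a terminated study of 136 randomized subjects reported in a synoptic CSR.

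A reader might also infer that affected placebo subjects end up with zero documented days overall. The SAP does not support that: maintenance days are still added, so a total of zero arises only when treatment ends during titration.

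**Conclusion.** The stated counting rule is wrong for this design. Followed literally, it understates compliance and interruption-excluded exposure in the placebo arm only. For one fully taken 14-day titration on the detailed form, the loss is 14 documented days: 14/168 = 8.3 percentage points at 168 days and 14/1092 = 1.3 points at 1092 days. For treatment lasting 70 to 1092 days, compliance falls from the 100% category to 80% to <99%. Interruption duration rises by the same 14 days, with a false flag where there was no gap. A placebo subject stopping in titration would show 0% compliance even though section 5.1.4 counts that subject as treated on the strength of a logged dose.

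The conclusion assumes a literal reading and applies only to detailed-form records. The number of such records is not given, so the effect on arm-level summaries cannot be sized. As a guide, if the 136 subjects split evenly (68 per arm, an assumption), each misclassified subject moves an arm's percentage by 1/68 = 1.5 points. Duration of Study Treatment and the EOT date rest on dates and do not change, and the efficacy analyses do not use this count. The point is worth correcting, but it does not threaten the trial's main results.

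**What to change.** In section 5.3.1.2.1, replace the restriction to the active dose form with: based on the up-titration study drug tablets (ponesimod or matching placebo). State that each detailed-form record contributes min(number of tablets taken, record end date − record start date + 1) in both arms, as for maintenance. The same rule should govern detailed-form records at re-initiation.

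The cost is one sentence in the SAP and about one line of programming. No dosing rule, data collection or other derivation changes, and there is no evident downside. If programs already exist, check that no filter on active drug has been applied to the detailed-form records.
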